**The effects of magnesium sulphate on intraoperative
blood loss in meningioma patient undergoing
craniotomy with tumor removal: A prospective
randomized study.**

NCT number: NCT03558516

Document date: 1 August 2018

Study protocol

The protocol was approved by the institutional ethics committee (SI 259/2018). After obtaining written informed consent from all patients, a randomized double-blinded placebo-controlled trial was conducted on 80 patients. This study was registered at Clinical Trials.gov (NCT03558516). The patients will be randomized into 2 groups in blocks of 4 by computer-generated numbers. The sequence numbers and groups will be placed inside concealed envelopes, which will be opened by researchers. The researchers will enroll the participants but will not take part in patient care.

We will enroll patients aged between 18-70 years, American Society of Anesthesiologist (ASA) grade I and II, diagnosed of supratentorial meningioma and underwent craniotomy with tumor removal at Siriraj hospital, Mahidol university. The exclusion criteria included all of the following conditions; preoperatively unstable hemodynamics requiring vasopressors or vasodilators, heart disease or heart block, liver disease Child Pugh Score C, Renal insufficiency or estimated glomerular filtration rate (e-GFR) < 60 mL/min, allergy history of magnesium or any drug use in study protocol, use calcium channel blocker before operation, pregnancy, receive magnesium sulfate to treatment other conditions, baseline serum magnesium more than 2.6 mg/dL, BMI > 30 kg/m², and prone to brain herniation from increased intracranial pressure.

On the day before surgery, the informed consent will be obtained and baseline cognitive function will be measured by Montreal Cognitive Assessment (MOCA) test.

At the operating room, standard monitorings will be used. General anesthesia will be inducted with propofol 1.5-2.0 mg/kg, fentanyl 1-2 mcg/kg, and then cis-atracurium 0.15 mg/kg will be given for facilitating tracheal intubation. Then, the extra-large bore intravenous lines will be accessed and radial artery will be cannulated for continuous arterial pressure monitoring. A baseline blood sampling for magnesium level will be obtained.

Group Mg (Study group) patients will receive 40 mg/kg of magnesium sulphate loading in 30 minutes at incision and then continuous drip 10 mg/kg/hr until dura will be closure. Group NSS (Control group) patients will receive normal saline with the same amount for loading and continuous infusion. Identical infusion syringes of magnesium (Mg) and placebo will be prepared and labeled by the research staff that will not provide care for the patients.

Anesthesia will be maintained with sevoflurane not exceeding 1 minimal alveolar concentration (MAC) with supplemental of intermittent fentanyl 0.5-1 mcg/kg, and continuous cis-atracurium 0.06-0.1 mg/kg/hr. If the depth of anesthesia is not adequate, propofol 2-6 mg/kg/hr continuous will be given.

Hematocrit levels will be measured every 2-3 hours. Intraoperative transfusion triggered for packed red cell is a hematocrit < 27%. Magnesium level will be measured at beginning and 4 hours. If magnesium level is more than 4 mg/dl, study drug will be stopped. Intraoperative bleeding will be measured by collection in suction bottle, plastic bags, drapes, and soaked gauzes subtracting the amount of irrigating fluid.

After the uneventful operation, the patients will be extubated and transferred to neurosurgical intensive care unit. Some patients will remain intubation and post-operative ventilation will be continued and reasons for remaining intubation will be noted.

Postoperative cognitive function test (MOCA) will be done at postoperative day 3-7 when patient has less pain and recover enough for comfortable testing.

The measure outcomes are intraoperative blood loss, amount of pack red cell (PRC) transfusion requirement, anesthetic requirement and postoperative MOCA score.

Study Protocol

The effects of magnesium sulphate on intraoperative blood loss in meningioma patient undergoing craniotomy with tumor removal: A prospective randomized study.

Special equipment preparation

1. Equipment for arterial line insertion for continuous BP monitoring
(A-line may be not required, according to anesthesiologist in charge)
2. Two syringe pumps for study drug and muscle relaxant administration
3. Study drug (be prepared by investigator)
4. Two heparin tubes (green capped tube)
5. Equipment for hematocrit assessment

Monitoring & IV access

- Standard monitoring (NIBP, Pulse oximetry, EKG, End tidal CO₂)
- Arterial line insertion (before or after induction)

Induction

- **Fentanyl 1-2 mcg/kg**
- **Propofol 1.5-2 mg/kg**
- **Cis-atracurium 0.15 mg/kg** then wait for 4 minutes before intubation
- Use Sevoflurane in Air:Oxygen 1:1, Sevoflurane < 1 MAC
- Positioning as usual
- Aspirate blood from A-line **3 ml** into heparin tube for assess baseline Mg level
(Aspirate from vein if no A-line)

Maintenance

- Prepare study drug in syringe pump
- At skin incision **Study drug 0.2 ml/kg loading drip in 30 minutes** for example BW 60 kg use drug $0.2 \times 60 = 12$ ml drip 24 ml/hr for 30 minutes then IV continuous **0.05 ml/kg/hr** for example BW 60 kg administer 3 ml/hr
- Use **Cis-atracurium IV continuous infusion 0.06-0.1 ml/kg/hr**
- Give intermittent **Fentanyl 0.5-1 mcg/kg/hr** according to anesthesiologist in charge
- If Depth of anesthesia is not adequate or brain is tight, you can use **Propofol 2-6 mg/kg/hr** according to anesthesiologist in charge
- Assess **Hematocrit before PRC transfusion**, PRC is transfused when Hct.<27%
- 4 hours after skin incision Aspirate blood from A-line **3 ml** into heparin tube for assess Mg level
(Aspirate from vein if no A-line)

Intraoperative hypotension	Intraoperative hypertension
SBP<90 mmHg or decrease <20% from baseline	SBP>140 mmHg or increase >20% from baseline
1. Fluid resuscitation or 2. Vasopressor according to anesthesiologist in charge	1. Increase Sevoflurane to 1 MAC wait for 5 min, if BP still high 2. Fentanyl 25 mcg not exceed 2 times, wait for 5 minute (total 10 mins) if BP still high 3. Propofol intermittent bolus or continuous drip if depth of anesthesia is not adequate 4. If depth of anesthesia is adequate, Nicardipine 0.2-0.4 mg in titration or Labetalol 2.5-5 in titration or Continuous drip according to anesthesiologist in charge

End of the case

- **Stop Study drug when dura was closure**
- Discontinue muscle relaxant at least 30 minute before operation finish
- **Record Intraoperative blood loss (Primary outcome)**

Reversal and Extubation

- **Use Glycopyrrolate 0.4 mg and Neostigmine 2.5 mg as reversal agents**
- If residual neuromuscular blocking effect is suspected, evaluate train of four before extubation
- Extubation when patients fully awake, open eyes and follow command
- **Record time when fully awake and extubation (Secondary outcome)**
- If remain intubation, please note the reason for remaining intubation

Step for sending lab investigation

- Send heparin tube to laboratory within 2 hours
- 8.00 am – 4.00 pm contact research officer
- After 6.00 pm contact Dr.[name]

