**The effects of magnesium sulphate on intraoperative
blood loss in meningioma patient undergoing
craniotomy with tumor removal: A prospective
randomized study.**

NCT number: NCT03558516

Document date: 1 August 2018

Statistical Analysis Plan

The collected data will be analyzed by Statistical Package for the Social Sciences (SPSS) software version 18.0 (SPSS Inc., Chicago, IL, USA). Data will be described in terms of frequencies (number and percent of cases), mean \pm standard deviation, median (range) when appropriate. Chi-square or Fisher's exact test will be used for comparing categorical data. Student's t-test will be used for comparing continuous data with normal distribution. Comparison of nonparametric variables will be done using Mann-Whitney test. The p-value < 0.05 will be considered statistical significance.

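### Red cell (PRC) amount depends on starting haematocrit as well as blood loss; no pre-incision haematocrit is specified and the SAP test is unadjusted, so some precision is lost

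*Protocol*

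**What the plan says.** - **Trigger.** The protocol narrative states "Intraoperative transfusion triggered for packed red cell is a hematocrit < 27" per cent. The operative sheet, under Maintenance, gives the same threshold.
- **Outcome.** The narrative's outcome list includes "amount of pack red cell (PRC) transfusion requirement". The sheet, under End of the case, marks intraoperative blood loss as the primary outcome, so PRC amount is non-primary.
- **Eligibility.** "We will enroll patients aged between 18-70 years, American Society of Anesthesiologist (ASA) grade I and II" opens the inclusion criteria. The exclusions cover kidney and liver function and "baseline serum magnesium more than 2.6 mg/dL, BMI > 30 kg/m²", among others. None concerns haematocrit or haemoglobin.
- **Baseline blood.** "A baseline blood sampling for magnesium level will be obtained", after induction. Magnesium is the only test named for it.
- **Haematocrit timing.** The narrative plans a reading every 2-3 hours and gives no starting point. The sheet says "Assess Hematocrit before PRC transfusion, PRC is transfused when Hct.<27" per cent and asks for no other reading.
- **Allocation.** 80 patients in two groups, in blocks of 4, with no stratification stated.
- **Analysis.** The SAP lists chi-square or Fisher, Student's t, and "Comparison of nonparametric variables will be done using Mann-Whitney test". It names no test for PRC in particular and no covariate for any outcome. A PRC amount with many zeros would go to the Mann-Whitney test.

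**The concern.** With a fixed trigger, two patients who bleed the same volume can receive different amounts of red cells only because one started nearer to 27%. That part of the variation in PRC has nothing to do with magnesium. In a trial of 80 with no stratification on haematocrit, it widens the uncertainty of the PRC comparison. It also allows a chance difference in starting haematocrit to push PRC in a direction that measured blood loss does not follow.

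The practical gap is the record. A team working from the sheet alone may hold no haematocrit for a patient who is never transfused. A team following the narrative may take its first reading well after incision. Such a reading already reflects bleeding and study drug, so it cannot serve as a baseline covariate. Without a pre-incision value, an imbalance can be neither checked nor adjusted for.

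**Working it through.** The plan gives no figure on this point to reproduce, and no effect size, SD or power accompanies the 80. **From the documents:** trigger 27%, N = 80, significance level 0.05. **Assumed:** 1:1 allocation (40 per arm), two-sided testing, and every haematocrit, blood volume and blood loss value below.

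**1. Does PRC depend on starting haematocrit (H)?** Take blood volume V = 60 kg × 65 ml/kg = 3,900 ml. The loss that brings H to 27% is V × ln(H/27) if lost volume is replaced continuously. The simpler V × (H − 27)/H gives a lower figure.

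| Starting H | V(H − 27)/H | V ln(H/27) |
|---|---|---|
| 28% | 139 ml | 142 ml |
| 30% | 390 ml | 411 ml |
| 36% | 975 ml | 1,122 ml |
| 40% | 1,268 ml | 1,533 ml |

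Over 50-70 kg and 65-75 ml/kg, the logarithmic formula gives 342-553 ml from 30% and 1,277-2,063 ml from 40%. The dependence is clear at any of these values.

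**2. How large can chance imbalance be?** The 95% range of the between-arm difference in mean H is ±1.96 × SD × √(2/40). For SD 3, 4 and 5 this is ±1.3, ±1.8 and ±2.2 points. From an assumed mean of 38, 3,900 × ln((38 + d)/38) turns these into about 130, 180 and 220 ml of bleeding margin. These are edge-of-range values. For scale, a 40% reduction from an assumed 600 ml median is 240 ml.

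**3. What does one covariate cost or gain?** Adjusted/unadjusted variance = (1 − r²) × (1 + 1/76), where r is the correlation of H with PRC amount and 76 = 80 − 4. Forty per arm detects (1.960 + 0.842) × √(2/40) = 0.626 SD at 80% power.

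| r | Variance ratio | Power at 0.626 SD |
|---|---|---|
| 0 | 1.013 | 79.4% |
| 0.1 | 1.003 | 79.8% |
| 0.2 | 0.973 | 81.0% |
| 0.3 | 0.922 | 83.0% |
| 0.5 | 0.760 | 89.5% |

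At r = 0 the cost is 80 × 1.013 ≈ 81, about one patient.

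**4. What does a threshold-transfusion simulation give?** All runs assume mean H 38, SD 3-5, lognormal blood loss and, under the alternative, a 40% reduction.

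- *Median loss 600-1,200 ml, 18 scenarios of 1,000 trials.* Adjusting the rank analysis of PRC units for H cut residual variance by 4-8% (SD 3), 8-14% (SD 4) and 11-23% (SD 5). Power rose by up to about 10 points; the best case was 68% to 78% (median 1,200 ml, log-SD 0.6, SD 5). The gain was about nil with highly variable loss and SD 3. Under no effect, rejection was 5.4% unadjusted and 5.5% adjusted (3,000 trials).
- *Median loss 500-1,200 ml, log-SD 0.7, 70 ml/kg, 3 haematocrit points per unit, 1,500 trials per scenario.* Power of Mann-Whitney → adjusted rank analysis:

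| SD of H | 500 ml | 800 ml | 1,200 ml |
|---|---|---|---|
| 3 | 24.6 → 23.7% | 47.5 → 48.6% | 67.2 → 69.0% |
| 4 | 23.7 → 23.7% | 45.7 → 49.1% | 61.0 → 67.0% |
| 5 | 21.4 → 23.5% | 40.4 → 44.8% | 57.0 → 65.5% |

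In this second set, r between H and PRC was −0.16 to −0.37, against 0.58 to 0.91 between blood loss and PRC. Linear adjustment cut the variance of the treatment difference by 0-14%. Null rejection was 4-6% with and without adjustment, and the mean difference agreed to within 0.01 units. After linear adjustment, residuals still correlated at 0.05-0.31 with the squared deviation of H, because the trigger is a threshold.

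**The case against.** The strongest reply is that nothing here threatens validity. Both arms share one trigger and allocation is randomised, so starting haematocrit is balanced in expectation. A reader might infer from the missing eligibility limit that the PRC comparison is biased by preoperative anaemia. The documents do not support that, and the null rejection rates and unmoved mean difference in the working speak against it. Chance imbalance is ordinary sampling error, already covered by the 0.05 level. This reply stands in full.

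Three other strong readings also fail:

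- *That a patient who starts just below 27% scores the same as a heavy bleeder.* The outcome is an amount, not transfused yes/no, and a rank test separates one unit from several.
- *That very low starters dominate.* With mean 38, the expected number of 80 below 27% is 0.01, 0.24 or 1.1 for SD 3, 4 or 5; at or below 28% it is 0.03, 0.5 or 1.8. ASA I-II may limit severe anaemia further, though the documents do not say so.
- *That no haematocrit is planned for untransfused patients.* The narrative's reading every 2-3 hours covers everyone. What is missing is a value fixed before incision, and agreement between narrative and sheet.

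It can also be said that adjusting a non-primary outcome for a gain between nil and modest is a matter of preference. That limits the weight of the point. It does not answer the missing baseline value, which may not be recoverable once the trial has run.

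**Conclusion.** The point holds as a cheap gain in precision for one non-primary outcome. The documents alone establish the fixed trigger, the absence of a haematocrit limit, the lack of a specified pre-incision value and the unadjusted test. The size of the gain rests wholly on assumed haematocrit and blood loss distributions: it is near zero if starting values are tightly grouped (SD 3) and approaches the upper end only at SD 5 with larger, less variable losses.

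A reader might expect adjustment to remove the dependence on starting haematocrit. It does not: most of the residual variance remains, and a single linear term fits a threshold-driven, zero-heavy amount imperfectly. The primary outcome, measured blood loss, is not affected by the transfusion trigger in this way.

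**What to change.** 1. **Protocol.** Name one pre-incision haematocrit for every patient, taken from the baseline sample already drawn for magnesium, and record it as trial data. Reconcile the haematocrit timings in the narrative and the operative sheet. Neither eligibility nor the trigger needs to change for this purpose.
2. **SAP.** Report pre-incision haematocrit by arm. Prespecify one PRC analysis: rank the PRC units over all patients (midranks for ties), regress the ranks on arm with pre-incision haematocrit as covariate, and test the arm term. Keep the plain Mann-Whitney test as the sensitivity analysis. Describe the result as a precision gain, not a bias correction.

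**Cost.** One extra recorded value per patient, from blood already drawn and with haematocrit equipment already on the sheet's preparation list, plus a sentence or two in the SAP. The downside is a model in place of a plain rank test and, if haematocrit proves uninformative, the loss of about one patient's worth of precision.

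### The working sheet prints the relative hypotension trigger with its inequality reversed (minor, wrong as written), and its cis-atracurium rate changes unit with no concentration stated

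*Protocol*

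**What the plan says.** The Protocol has a narrative part and a working sheet for operating-room staff, which starts at *Special equipment preparation* and ends with the laboratory steps. The blood-pressure table follows the *Maintenance* list on the sheet.

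- Hypotension is "SBP<90 mmHg or decrease <20% from baseline", and the response is "1. Fluid resuscitation or 2. Vasopressor according to anesthesiologist in charge".
- Hypertension is "SBP>140 mmHg or increase >20% from baseline". The response starts with "1. Increase Sevoflurane to 1 MAC wait for 5 min, if BP still high" and goes on to fentanyl, propofol, and then nicardipine or labetalol.

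Neither the Protocol narrative nor the SAP gives any other intraoperative blood-pressure threshold, so nothing elsewhere corrects the cell.

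For the muscle relaxant, the narrative gives "continuous cis-atracurium 0.06-0.1 mg/kg/hr" and the *Maintenance* list gives "Cis-atracurium IV continuous infusion 0.06-0.1 ml/kg/hr". The equipment list calls for "Two syringe pumps for study drug and muscle relaxant administration". Neither document states a cis-atracurium concentration.

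**The concern.** The two cells of the table are meant to mirror each other, one for low and one for high pressure. The absolute limits do. The relative limits do not: the high-pressure cell asks for a rise of more than 20%, and the low-pressure cell for a fall of less than 20%. Taken at its word, the low-pressure cell treats trivial falls as hypotension and leaves out the larger falls it should catch, unless the reading is also below 90. At some baselines a reading can also meet both columns, whose treatments pull in opposite directions.

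The table is an operative treatment threshold on the page that staff follow during surgery, so it should be right as printed.

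The relaxant line matters for a related reason. From the documents alone, staff cannot confirm that the pump rate on the sheet delivers the dose in the narrative.

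**Working it through.** **Inputs.** The limits of 90 mmHg, 140 mmHg and 20% come from the table. The documents give no baseline systolic pressures, so every baseline B below is an assumption. Readings are whole mmHg.

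**Rules.**
- Hypotension as printed: SBP < 90, or 0.8B < SBP < B.
- Hypotension with the sign reversed: SBP < 90, or SBP < 0.8B.
- Hypertension: SBP > 140, or SBP > 1.2B.

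**Readings on which the rules differ.**
- *Over-triggered* (printed rule treats, corrected rule does not): from 90 or just above 0.8B, whichever is higher, up to just below B.
- *Missed* (corrected rule treats, printed rule does not): from 90 to just below 0.8B. This needs 0.8B > 90, that is B > 90/0.8 = 112.5.
- *Both columns as printed*: SBP above 140 and above 0.8B, but below B. This needs B > 140.

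| Assumed B | 0.8B | Over-triggered | Missed | Both columns, as printed |
|---|---|---|---|---|
| 110 | 88 | 90-109 (20 readings) | none | none |
| 120 | 96 | 97-119 (23) | 90-95 (6) | none |
| 130 | 104 | 105-129 (25) | 90-103 (14) | none |
| 140 | 112 | 113-139 (27) | 90-111 (22) | none |
| 150 | 120 | 121-149 (29) | 90-119 (30) | 141-149 (9) |
| 160 | 128 | 129-159 (31) | 90-127 (38) | 141-159 (19) |

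A fall of exactly 20% (96 at B = 120) meets neither version of the relative rule. In the last column the falls are small: 1/150 = 0.7% to 9/150 = 6.0% at B = 150, and 1/160 = 0.6% to 19/160 = 11.9% at B = 160.

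The missed range needs care. A pressure that falls steadily passes through the 0-20% band first and would already have triggered treatment. The gap therefore matters only for an abrupt fall, or if treatment were withdrawn once the fall passed 20%.

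**After the sign is corrected.** Both columns are met when 140 < SBP < 0.8B, which needs B > 140/0.8 = 175. At B = 180 (0.8B = 144) that is 141-143; at B = 190 (0.8B = 152) it is 141-151. There is no overlap for baselines tested from 110 to 175.

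**Units: the study drug first.** The sheet's study-drug volumes can be reconciled with the narrative. The loading dose gives 40 mg/kg ÷ 0.2 ml/kg = 200 mg/ml, and the maintenance dose gives 10 mg/kg/hr ÷ 0.05 ml/kg/hr = 200 mg/ml. The 60 kg example also reproduces: 0.2 × 60 = 12 ml, 12 ÷ 0.5 hr = 24 ml/hr, and 0.05 × 60 = 3 ml/hr.

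**Units: cis-atracurium.** At 60 kg the narrative gives 0.06 × 60 = 3.6 to 0.1 × 60 = 6 mg/hr, and the sheet gives 3.6 to 6 ml/hr. At a syringe concentration of c mg/ml, the sheet delivers c times the narrative dose, so they agree only at c = 1. Because c is not stated, these values are assumptions:

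| Assumed c (mg/ml) | Dose from the sheet (mg/kg/hr) |
|---|---|
| 0.5 | 0.03-0.05 |
| 1 | 0.06-0.1 |
| 2 | 0.12-0.2 |
| 5 | 0.3-0.5 |

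The induction dose is given in mg/kg only, so it does not reveal the concentration.

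**The case against.** The strongest reply is that this is a typing slip whose meaning nobody would mistake. The cell stands under a hypotension heading, directly after SBP < 90 and beside a rise of more than 20%. Nothing suggests that an anesthesiologist would treat a 1% fall and ignore one of 25%, and treatment is left to that person's judgement. All of this stands, and it is why the point is minor. It does not make the printed rule right. The discretion concerns how to treat, whereas the threshold that defines the event is printed as fixed.

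A second reply is that the double-column case is conditional. This also stands. It needs a baseline above 140, and the documents do not show how common that is.

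A third reply is that a volume rate is natural on a sheet written for a syringe pump, and that the relaxant figures reconcile at 1 mg/ml. That is fair. The two lines may well agree in practice, but the documents do not let a reader confirm it.

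Three stronger readings are tempting, and the documents support none of them:

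- *The relaxant is given at the wrong dose.* With no concentration stated, an error is no more shown than agreement is.
- *The reversed sign biases the comparison or alters blood loss.* The same sheet applies to both arms of a trial described as double-blind, and nothing shows that the rule was followed literally or acted differently by arm.
- *The sheet omits a safety stop and needs new routing for magnesium results.* The narrative already has the stop: "If magnesium level is more than 4 mg/dl, study drug will be stopped". Not repeating it on the sheet is not an error. Nothing shows that magnesium levels reach the treating team, and withholding a high level from the clinician who judges readiness for extubation would not be a clear safety gain.

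**Conclusion.** The point holds as a minor correction of text that is wrong as written. It is not a design choice. The sign error is certain from the wording and the cell beside it, and no other part of the documents puts it right. Its literal size depends on the assumed baseline: at 120 mmHg, 23 readings are over-triggered and 6 are missed. The practical size is probably small, because the intended meaning is plain to most clinicians.

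The cis-atracurium mismatch is a secondary inconsistency. It is real on the page but unresolved as to dose, because it depends on a concentration that is not given. Neither item shows a dose error, a bias or an effect on the primary outcome.

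**What to change.** On the Protocol's working sheet:

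1. In the hypotension cell, change the sign before 20% from < to >, so that the relative trigger is a decrease of more than 20% from baseline.
2. Add one line saying which column takes precedence when a reading meets both. After step 1 this covers the overlap left at baselines above 175. The choice of column is a clinical one for the investigators.
3. Give the cis-atracurium infusion as 0.06-0.1 mg/kg/hr, as in the narrative, or keep an ml rate and state the syringe concentration that makes it match.

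The cost is one corrected page: one character, one line, and one unit or concentration. Design, sample size and analysis do not change.

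### Do the narrative outcome list and the operating-room sheet conflict over awakening and extubation time in a way that needs a change?

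*Protocol*

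**What the plan says.** The narrative part of the protocol closes with an outcome sentence: "The measure outcomes are intraoperative blood loss, amount of pack red cell (PRC) transfusion requirement, anesthetic requirement and postoperative MOCA score". It ranks none of the four.

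The second part of the protocol is a step-by-step sheet for the operating room. Under End of the case it has "Record Intraoperative blood loss (Primary outcome", and under Reversal and Extubation it has "Record time when fully awake and extubation (Secondary outcome". These are the only places where an outcome is called primary or secondary.

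On patients not extubated at the end of surgery, the two parts agree. The narrative says "Some patients will remain intubation and post-operative ventilation will be continued and reasons for remaining intubation will be noted" and the sheet says "If remain intubation, please note the reason for remaining intubation".

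The SAP assigns tests by type of data: chi-square or Fisher's exact, Student's t, or Mann-Whitney. It adds "The p-value < 0.05 will be considered statistical significance". Apart from its title, it names no outcome.

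**The concern.** Read as two outcome lists, the texts share only blood loss. Awakening and extubation time is a secondary outcome in one and absent from the other, and nothing in these two documents says which governs. After unblinding, a team could leave out a recovery delay by pointing to the narrative, or present a chance difference as a planned secondary result by pointing to the sheet. It is the only listed outcome that measures speed of recovery.

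The item is also thinly defined. No start is given for the interval. The sheet mentions several events that might serve: "Stop Study drug when dura was closure", "Discontinue muscle relaxant at least 30 minute before operation finish", and the end of the operation itself. It does not say whether awakening and extubation are one time or two, or how patients left intubated enter the comparison. If only observed times were tested, and slow waking was the reason for leaving patients intubated, a delay could be understated.

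**Working it through.** **1. The texts side by side.**

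| Item | Narrative | Operating-room sheet | SAP body |
|---|---|---|---|
| Blood loss | listed, unranked | primary | not named |
| Red-cell transfusion | listed | no outcome label | not named |
| Anaesthetic requirement | listed | no outcome label | not named |
| MOCA score | listed | absent | not named |
| Awakening and extubation time | absent | secondary | not named |

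The sheet covers equipment, induction, maintenance and reversal. A cognitive test on postoperative day 3-7 would not be expected there, so its absence says nothing about outcome status. The labels on the sheet mark what must be written down in theatre. No row has one part denying what the other asserts. The discrepancy is one item missing from one sentence. The union is 4 + 1 = 5 outcomes, or 6 if awakening and extubation are separate times.

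**2. What one more outcome costs.** The SAP gives no family-wise figure to reproduce. For k independent tests at 0.05 with no true effect, the chance of at least one false positive is 1 - 0.95^k:

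- k = 3: 1 - 0.8574 = 14.3%
- k = 4: 1 - 0.8145 = 18.5%
- k = 5: 1 - 0.7738 = 22.6%
- k = 6: 1 - 0.7351 = 26.5%

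If blood loss is primary and the other three narrative outcomes are secondary, adding one time moves 14.3% to 18.5%. Counting all four narrative outcomes, it moves 18.5% to 22.6%. Either way the step is about four points. Two times take the three secondaries to 22.6% if independent, and to 19.8-20.9% if the pair correlates at 0.95 to 0.8. The 5% level for blood loss alone does not change.

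**3. Start of the interval.** This needs assumed inputs: 40 per arm (80/2), log-normal waking time with median 8-20 min and log-SD 0.6, true ratio 1.5, relaxant stopped 30 min plus an exponential interval of mean 10 min before the end, and dura closed 60 ± 15 min before the end. Simulated Mann-Whitney power is then 83% from the end of the operation, 42-70% from relaxant stop and 22-53% from dural closure. With no effect, taking the best of the three gives 11-13% instead of 5%. Of these inputs, only the total of 80 and the 30-minute minimum come from the documents. The protocol gives dural closure and relaxant stop as care steps and presents neither as a time origin.

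**4. Patients left intubated.** At log-SD 0.6 and ratio 1.5:

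- Unrelated reasons, 10% per arm dropped: power 79% against 84% with all times known, and the ratio stays at about 1.5.
- Slow waking as the reason, cut at the slowest 10% of controls: power 53% against 84%, apparent ratio 1.28.

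The second case implies a marked imbalance. The control cut lies at z = 1.282. The treated arm is shifted by ln(1.5)/0.6 = 0.676, so the fraction beyond the cut is the upper tail at 1.282 - 0.676 = 0.606, or about 27%. That is roughly 11 of 40 on magnesium against 4 of 40 controls. At log-SD 0.4 and 1.0 the fractions are 39% and 19%. At medians of 8-20 min the cut falls at 8 × exp(1.282 × 0.6) = 17 min to 20 × 2.158 = 43 min, an extubation cut-off that neither document contains. Neither document says that these patients will be dropped.

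**The case for a change.** The strongest case is that the narrative sentence reads as a complete list. The sheet's purpose explains why MOCA is missing there, but not why the narrative omits something the sheet calls an outcome. Both sentences are intact, so lost text is not the explanation. Settling the list, the start and the handling of patients left intubated would take a few sentences and remove room for choice after unblinding.

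The omission stands, and so does the absence of a stated start. The rest is weaker. Leaving the time out of the report would depart from a protocol that calls it a secondary outcome, and reporting it as secondary is what that protocol says. Harmonising the list would not alter any recorded datum or any test.

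A rule for patients left intubated is a trade-off, not a clear gain. Using late extubation times that reflect ventilation for surgical reasons costs power: 43% against 72% if those patients are dropped, at 20% per arm and log-SD 0.6. Comparing the proportions left intubated has little power at 40 per arm: Fisher's exact test gives 16% for 10% against 20%, and 53% for 10% against 30%. With 4 of 40 in one arm, significance needs 12 of 40 in the other (p = 0.048), so even 4 against 11 would fall just short. It would still be visible in the counts and recorded reasons.

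**Conclusion.** No change follows. This is an incomplete outcome sentence plus a definition that analysts can fill sensibly. Followed as written, the plan has the time recorded, the reasons for continued intubation noted, and a test available for each kind of data. Taking the two parts of the protocol together, with the end of the operation as the natural start and awakening and extubation reported separately, needs nothing the documents forbid.

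The cost that can be shown without outside inputs is about four percentage points of family-wise error per added outcome, under independence and no adjustment, and it falls on the secondary outcomes only. The larger figures for choice of start and for slow waking rest on assumed waking times, intervals and intubation rates, so they show what could happen and not a fault in the plan. The conclusion assumes that the sheet is read as part of the protocol. The protocol also says that the trial was registered; the registered outcome list was not available here, and nothing above depends on it.
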